**Reconstitution:**

N/A

**Administration:**

Add required dose to 60mL sodium chloride 0.9% and administer intravenously over 2 hours. Invert syringe to mix gently. CAMPATH should be administered under the supervision of a doctor. In order to assure complete delivery of CAMPATH, the line will be flushed with a minimum of 10mL 0.9% sodium chloride following completion of the CAMPATH infusion. To do this, attach another syringe to the syringe pump and administer the solution at the same rate as the previous infusion

During storage vials must be protected from light. Once diluted, infusion does not need to be protected from light during 2 hour administration time. However if not being administered immediately after dilution the infusion should be protected from light until it is administered, otherwise the antibody may start to deteriorate.

If infusion related side-effects occur infusion time can be increased up to 8 hours from time of reconstitution of CAMPATH for infusion.

**Compatible Infusions:**

Sodium Chloride 0.9%.

**Cautions/Side Effects:**

Exercise caution in the handling and preparation of the solution. Gloves must be worn. There is no information relating to the use of CAMPATH in pregnancy. As a precaution the company recommend it should not be handled by women who are pregnant or planning pregnancy. However the use of gloves will ensure there is no drug contact to staff. Safety glasses should be worn to avoid exposure in case of breakage or spillage.

Side-effects common with the first dose and include fever, rigors, headache, nausea, vomiting, rash, urticaria, pruritis, dyspnoea, hypotension and diarrhoea. Infusion related fever commonly begins 5-6 hours after infusion starts. More severe reactions such as bronchospasm and severe hypotension have been seen in a few instances and late hypotension can occasionally be a problem.

Thrombocytopenia most common during weeks 2-4 and neutropenia common between weeks 4-8.

*Treatment of side-effects:*

Side effects can be controlled by slowing or temporarily stopping the infusion. Administer PRN medication (paracetamol PO, chlorphenamine IV, hydrocortisone IV) if necessary.

Nebulised salbutamol may be required for bronchospasm.

If hypotension develops, hydration with normal saline is indicated, unless contraindicated based on underlying cardiac status.

**Other information:**

The CAMPATH will be administered as soon as possible post-reperfusion of the transplanted organ, once patient is haemodynamically stable. In some circumstances administration may be delayed until patient is in theatre recovery.

- IV methylprednisolone 500mg will be administered intraoperatively prior to organ reperfusion.
- 15-30 minutes before administer CAMPATH give 10mg IV chlorphenamine.
- Give CAMPATH 30mg IV over 2 hours once patient is haemodynamically stable. CAMPATH infusion should be completed within 3 hours post organ reperfusion. Where the patient is unstable and the administration is delayed, CAMPATH infusion must be complete within a maximum 6 hours after organ reperfusion.

#### 4.8.2 Subcutaneous administration

##### First dose

- Methylprednisolone 500mg IV prior to reperfusion of first organ
- Chlorphenamine 10mg IV 15-30minutes before SC alemtuzumab
- Immediately after first organ reperfusion give 30mg/1mL SC CAMPATH

##### Second dose (24 hours later)

- No pre-medication with steroid or antihistamine is generally necessary (but can be given at local investigators discretion)
- CAMPATH 30mg/1ml SC post transplant, 24 hours after first dose.

Side effects with SC CAMPATH: local irritation (e.g. erythema, rash) at the injection site is common.

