## 1.7 Two randomisations provides an efficient method of answering two important questions

The aim of the 3C study is to test two hypotheses:

- is CAMPATH-based induction therapy superior to standard IL-2 receptor antagonist-based induction?
- does a switch to sirolimus-based maintenance immunosuppression at six months post-transplant preserve graft function more effectively than remaining on CNI-based therapy?

In order to test the first hypothesis, all study participants will initially be randomly allocated to receive either CAMPATH- or basiliximab-based induction therapy. Patients allocated to receive CAMPATH induction (arm 1) will be given two doses of 30mg 24 hours apart. However, patients over the age of 60 will only be given the first 30mg dose (to avoid over-immunosuppression). For the next six months, these patients will receive low-dose tacrolimus (target level 5-7 ng/mL) and MPA (360mg bd).

Patients who receive standard basiliximab induction (arm 2) will receive standard dose tacrolimus (target levels 5-12 ng/mL), mycophenolate (MPA, 540 to 720mg bd) and corticosteroids (which will be reduced gradually to 5mg od, and withdrawn at the local investigator's discretion). These two groups (arms 1 and 2) can then be compared to compare the effect of a strategy of CAMPATH-based induction with a strategy based on standard IL-2 receptor antagonist induction.

In order to test the second hypothesis, six months after transplantation patients will be also be randomly allocated to either remain on tacrolimus-based maintenance therapy or to change to a sirolimus-based regimen. Patients allocated to tacrolimus will have a target trough tacrolimus level of 5-7 ng/mL, and those patients allocated to sirolimus will have a target trough sirolimus level of 6-12 ng/mL for the first six months, then reducing to 5-10 ng/mL. These two groups can then be compared to investigate whether or not sirolimus does preserve graft function better than low-dose CNI-based maintenance therapy.

---

 If mycophenolate sodium cannot be prescribed for local reasons, a dispensation can be made to allow mycophenolate mofetil to be substituted (see Appendix 9: Mycophenolate dosing for equivalent dosing).

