### 3.2.4 *Random allocation of study treatment*

Eligible and consenting individuals will then be randomised to study treatments. The study IT system will minimise the randomisation with respect to important patient characteristics (42). The study staff will be informed which induction therapy the patient is to receive (CAMPATH- or basiliximab-based induction) and given the patient's unique study reference.

The randomisation procedure will use minimized randomisation in order to ensure that treatment groups are balanced with respect to prognostically significant variables. The minimization variables will be:

- Recipient age: ≤30, 31-59, ≥60 years old;
- Ethnicity: white, non-white;
- Type of transplant: cadaveric heart-beating donor, non-heart-beating donor, living donor;
- HLA mismatch: as per current UK Transplant protocol:
  - 0-0-0 (HLA A-B-DR) mismatch;
  - 0 DR mismatch and 0-1 B mismatch;
  - 0 DR mismatch and 2 B mismatch, or 1 DR mismatch and 0-1 B mismatch;
  - 1 DR mismatch and 2 B mismatch, or 2 DR mismatch and 0-2 B mismatch;
- patient sensitisation status: 'highly sensitized' defined, for example, by a positive cross-match with 85% of donors (reaction frequency >85%).
- centre

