### 3.2.5 *Reducing dose of CAMPATH in elderly*

In view of concerns of over-immunosuppression in the elderly (and in particular the risk of post-transplant lymphoproliferative disorder in this group) the total dose of CAMPATH will be reduced in those ≥60 years old. These patients will not receive the second 30mg dose of CAMPATH.

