## 4.2 Appendix 2: Detailed treatment schedules

### 4.2.1 Induction treatments:

	Day 0	Day 1	Day 2	Day 3	Day 4-	Month 6	Month 12
ALLOCATION TO CAMPATH INDUCTION							
TRANSPLANT SURGERY							
Tacrolimus				2mg bd PO	Target trough level 5-7 ng/mL	See 4.2.2	
Steroids	500mg IV methylprednisolone pre-reperfusion						
CAMPATH	30mg IV  prior to reperfusion (within 15-30 minutes of methylprednisolone)	30mg IV 24h after first dose (unless patient >60 years old)					
Other	10mg chlorphenamine IV 15-30 mins prior to CAMPATH	10mg chlorphenamine IV 15-30 mins prior to CAMPATH 1g paracetamol 30-60 mins prior to CAMPATH					
MPA	360mg pre-op PO	360mg bd PO				360mg bd PO	180mg bd PO
ALLOCATION TO BASILIXIMAB INDUCTION							
TRANSPLANT SURGERY							
Tacrolimus	0.05 - 0.1mg/kg bd PO	Target trough level 5-12 ng/mL				See 4.2.2	
Steroids	500mg IV methylprednisolone pre-reperfusion	15-20 mg pre-op PO, then reduced (see section 4.2.1.1)					
Basiliximab	20mg 1h pre-op IV				20mg IV		
MPA	540 - 720mg pre-op	540 - 720mg bd				540 - 720mg bd	540 - 720mg bd PO

 See Appendix 8 for guidelines for administration of CAMPATH

 If a centre wishes to administer CAMPATH subcutaneously they may do so in all their patients.

 If mycophenolate sodium cannot be prescribed for local reasons, a dispensation can be made to allow mycophenolate mofetil to be substituted (see Appendix 9: Mycophenolate dosing for equivalent dosing).

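### The age cut-off for omitting the second CAMPATH dose differs between sections (≥60 versus over 60), and the subcutaneous instructions in 4.8.2 omit it altogether

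*Protocol*

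**What the plan says.** Four places in the protocol bear on who receives the second CAMPATH dose.

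- **Section 3.2.5**, the section devoted to dose reduction in older patients, states that "the total dose of CAMPATH will be reduced in those ≥60 years old" and then that "These patients will not receive the second 30mg dose of CAMPATH". It names no route of administration.
- **Section 1.7** states that "patients over the age of 60 will only be given the first 30mg dose (to avoid over-immunosuppression". It also names no route.
- **Section 4.2.1 (Appendix 2)**, the treatment schedule, has in its Day 1 cell: "30mg IV 24h after first dose (unless patient >60 years old". Footnote 7 to the CAMPATH row reads "See Appendix 8 for guidelines for administration of CAMPATH", and footnote 8 reads "If a centre wishes to administer CAMPATH subcutaneously they may do so in all their patients".
- **Section 4.8.2 (Appendix 8)**, on subcutaneous administration, has its own second-dose block with the instruction "CAMPATH 30mg/1ml SC post transplant, 24 hours after first dose". It gives no age condition and no cross-reference to 3.2.5 or Appendix 2.

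Two further sections matter for reading these. Section 3.13.4 refers the reader to Appendix 2 for study drug doses. Section 3.2.4 sets the minimisation bands as "Recipient age: ≤30, 31-59, ≥60 years old".

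**The concern.** There are two separate problems.

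The first is the cut-off. A rule written as ≥60 includes a patient aged 60. A rule written as over 60 or >60 does not, if age is counted in completed years. A site that follows the Appendix 2 schedule correctly would therefore give a 60-year-old a dose that 3.2.5 says must be withheld. This applies to intravenous and subcutaneous use alike.

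The second is the silence in 4.8.2. It reads as a working sheet with premedication, dose and timing. It restates the second dose but not the restriction. The Appendix 2 cell that carries the exception is worded for the intravenous route, so no text specific to the subcutaneous route contains an age rule.

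The restriction exists for safety: 3.2.5 gives over-immunosuppression, and lymphoproliferative disorder in particular, as the reason. A dose given in error cannot be undone, since section 1.4 describes T cells as severely depressed for up to 18 to 24 months after CAMPATH. Central checks may not catch an error either, because section 4.2.4.3 says the coordinating centre will not monitor detailed implementation of the treatment schedules.

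**Working it through.** No sample size, power or error-rate figure is involved, so there is no planned figure to reproduce. The check is to apply each text literally at the ages around the cut-off and compare the total dose.

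**Inputs.** Each dose is 30 mg (1.7, Appendix 2, 4.8.2). One dose totals 30 mg and two doses total 2 × 30 = 60 mg.

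**Reading of age.** The protocol does not define it. The 3.2.4 bands run from 31–59 straight to ≥60, which leaves no gap only if age is in completed years. That reading is used here.

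| Text | Who gets one dose only | Age 59 | Age 60 | Age 61 and over |
|---|---|---|---|---|
| 3.2.5 | ≥60 | 60 mg | 30 mg | 30 mg |
| 1.7 | over 60 | 60 mg | 60 mg | 30 mg |
| Appendix 2, Day 1 | >60 | 60 mg | 60 mg | 30 mg |
| 4.8.2, read alone | no condition stated | 60 mg | 60 mg | 60 mg |

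**Results.**

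- Age 59: all four texts agree on 60 mg.
- Age 60: 3.2.5 gives 30 mg and the other three give 60 mg.
- Age 61 and over: 3.2.5, 1.7 and Appendix 2 agree on 30 mg; only 4.8.2 read alone gives 60 mg.
- Wherever the texts differ, the difference is 60 − 30 = 30 mg, which is the whole second dose.

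**Sensitivity to the reading of age.** If age were taken exactly rather than in completed years, >60 and ≥60 would differ only on the 60th birthday itself, and the conflict between 3.2.5 and Appendix 2 would nearly vanish. The omission in 4.8.2 would be unchanged.

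**Can 4.8.2 be reached for older patients?** Yes. Footnote 8 lets a centre use the subcutaneous route for all its patients. That footnote concerns route, though. It does not lift the Day 1 age exception in the same table row.

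**Which cut-off fits the rest of the protocol?** The minimisation bands put a 60-year-old in the older group, as 3.2.5 does. That supports ≥60 as the intended cut-off.

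**The case against.** The strongest reply concerns 4.8.2. Section 3.2.5 is a dedicated rule that names no route, so it already covers subcutaneous dosing. Appendix 8 is an administration guide and does not set the number of doses: its intravenous part (4.8.1) has no second-dose instruction at all, so read alone it would give every intravenous patient a single dose. It has to be read with Appendix 2, and the footnotes that lead to it sit in the very row that carries the age exception. On that view the second-dose block only explains how to give the dose when it is due. Most of this stands. The omission in 4.8.2 is missing detail, not a contrary rule, and it matters only if staff use that page by itself.

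On the cut-off, it can be said that the wording in 1.7 is ambiguous for someone past their 60th birthday, that completed years is an inference, that 4.2.4.3 describes the schedules as guidance so a firm rule in the main text should prevail, and that only patients aged 60 in the CAMPATH arm are concerned. The conflict is indeed that narrow, and 1.7 is the less certain of the two discrepant texts. But >60 in Appendix 2 against ≥60 in 3.2.5 remains a plain disagreement under the natural reading. The protocol nowhere says which prevails, and 3.13.4 sends staff to the table with >60.

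The consequences are also limited. A total of 60 mg is the trial's own regimen for younger patients, and section 1.4.2 describes retrospective data on lymphoproliferative disorder as reassuring.

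**Conclusion.** The point holds and should be corrected. The firmer part is the cut-off: in completed years, a 60-year-old allocated CAMPATH is assigned 30 mg by 3.2.5 and 60 mg by Appendix 2, with 1.7 on a plain reading siding with Appendix 2. The weaker part is that 4.8.2 restates the second dose without the age restriction, which creates a risk only when that section is used alone.

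The size is one 30 mg dose per affected patient. The number affected cannot be estimated, because the documents give neither the number of centres using the subcutaneous route nor the expected number of patients aged 60 or over. The conclusion on the cut-off assumes age in completed years, as the minimisation bands imply. Neither part has any bearing on sample size, power or the planned analyses.

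**What to change.** Three edits to the protocol:

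1. In 1.7, change the condition to 60 years or over.
2. In the Appendix 2 Day 1 cell, change >60 to ≥60.
3. In the second-dose block of 4.8.2, add: *Do not give to patients aged ≥60 years (see section 3.2.5).*

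This matches 3.2.5 and the minimisation band in 3.2.4. If the sponsor intends a different cut-off, that one should appear in all four places (1.7, 3.2.5, Appendix 2 and 4.8.2). The cost is one added line and two aligned thresholds, with no new data, patients or design change.

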#### 4.9 Appendix 9: Mycophenolate dosing

The following table gives the equivalent doses of mycophenolate sodium and mycophenolate mofetil (which can be used if MPA is not available).

Mycophenolate sodium	Mycophenolate mofetil
180 mg	250 mg
360 mg	500 mg
540 mg	750 mg
720 mg	1000 mg

Campath, Calcineurin inhibitor reduction and Chronic allograft nephropathy

Data Analysis Plan for assessing clinical efficacy and safety of sirolimus-based maintenance treatment in the 3C Study

1 Background

This Data Analysis Plan describes the strategy, rationale and statistical methods that will guide assessment of the clinical efficacy and safety of sirolimus-based maintenance therapy in the 3C Study. A separate Data Analysis Plan will describe the assessment of Campath-based induction therapy. All analyses and reports will be prepared by the coordinating centre in the Clinical Trial Service Unit, University of Oxford.

The 3C Study is a randomized trial investigating two strategies to improve long-term outcomes in kidney transplantation. Firstly, it is comparing Campath (alemtuzumab) with basiliximab as the basis of induction therapy. Secondly, it is comparing an elective conversion to sirolimus-based maintenance therapy at around 6 months after transplantation compared to remaining on tacrolimus-based maintenance therapy. Follow-up visits are scheduled at 1, 3, 6, 9 and 12 months after transplantation and will then be followed by annual mailed questionnaires. In addition, all participants will be flagged with various NHS registries.

2 Comparisons of sirolimus-based versus tacrolimus-based maintenance therapy

All comparisons will involve comparing outcome during the defined analysis period among all those participants allocated at the maintenance randomization to receive sirolimus-based induction versus all those allocated to receive tacrolimus-based maintenance therapy (i.e. “intention-to-treat” analyses).^{1, 2} All analyses will be stratified by induction therapy arm.

2.1 Primary comparison

The primary comparison will be of graft function (estimated using the 4 variable MDRD formula) at 2 years after transplantation. Any surviving participants with no valid values of creatinine (and hence eGFR) in this time window will be defined as having missing values and imputed as described in section 3.1 below). Values at 3, 6, 9, 12 and 15 months after randomization will also be presented but not compared.

2.2 Secondary comparisons

The secondary comparisons will be of the incidence of the first occurrence (after maintenance randomisation) of:

- i. Graft outcomes:
 - a. Graft rejection

- i. Biopsy-proven acute rejection: cellular (subdivided into Banff 1, 2, 3 and unknown), humoral (subdivided into Banff 1, 2, 3 and unknown) and all³
 - ii. All rejection: presumed and biopsy-proven (as above)
 - b. Graft survival (with reasons for failure subdivided into glomerular disease, fibrosis/atrophy, medical/surgical condition, rejection or unknown)
 - ii. Safety outcomes:
 - a. Serious infections
 - i. All serious infections: subdivided into opportunistic and non-opportunistic
 - ii. Opportunistic infections subdivided into CMV, BK, fungal (non-invasive and invasive) and other (PCP, mycobacterial and other)
 - iii. Non-opportunistic subdivided into urinary tract, respiratory, gastrointestinal, central nervous system, other/unknown
 - b. Cancer
 - i. All cancer: subdivided into haematological (including post-transplant lymphoproliferative disorder and other); skin (subdivided into non-melanoma and melanoma); lung; gastrointestinal; hepatobiliary; breast; prostate; other/unspecified
 - iii. Other outcomes of interest
 - a. Major vascular events (composite of non-fatal myocardial infarction, cardiac death, non-fatal or fatal stroke and arterial revascularisation)
 - b. Death: subdivided into vascular, infection, cancer and other causes
 - c. Composite of death or graft failure
 - d. Post-transplant diabetes mellitus
 - e. Serious adverse events (subdivided into respiratory, gastrointestinal, hepatobiliary, cardiovascular, musculoskeletal, skin, genitourinary, haematological, other transplant-related, other/unspecified)
 - f. Incidence of anaemia (defined as Hb < 13 g/dL in men, <12 g/dL in women) and severe anaemia (defined as Hb <11 g/dL in men, <10 g/dL in women) [at 3 and 6 months post-randomization only]
 - g. Incidence of leucopenia (defined as total white cell count <3 x 10⁹ cells/mm³) [at 3 and 6 months post-randomization only]
 - h. Incidence of neutropaenia (defined as neutrophil count <2 x 10⁹ cells/mm³) and severe neutropaenia (defined as neutrophil count <1 x 10⁹ cells/mm³) [at 3 and 6 months post-randomization only]
 - i. Incidence of thrombocytopaenia (defined as platelet count <75 x 10⁹ cells/mm³) [at 3 and 6 months post-randomization only]
 - j. Levels of immunosuppressants at 3, 6, 12 and 18 months after randomisation
 - k. Proteinuria (compared by calculating ratio of geometric means) [at 3 and 6 months post-randomization only]. If albumin:creatinine ratio (ACR) value is available but not protein:creatinine ratio (PCR) for a given time-point, then it will be converted to PCR by the formula PCR = ACR x 1.6
 - l. Total cholesterol, HDL-cholesterol, non-HDL-cholesterol and triglyceride concentrations, and use of lipid-lowering therapy [at 6 months post-randomization only]
 - iv. Tolerability

- a. Reasons for stopping allocated treatment subdivided into suspected serious adverse reactions, serious adverse events (subdivided as in iii.e above), non-serious adverse reactions (including proteinuria, deteriorating graft function and other NSARs in same categories as SAEs) and other reasons (patient wishes or other)

These analyses will be conducted when all participants have completed 2 years and at a median follow-up of 5 years after transplantation. Participants will be censored at the date at their date of death or the date on which they were last known to be alive (based on flagging with the Office for National Statistics) once 2 (or 5) years have elapsed after the last patient was transplanted.

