### 2.2 TREATMENT COMPARISONS

Study medications will not be blinded as this will not be practical. The effects of CAMPATH on the lymphocyte count are readily apparent, and are not shared with basiliximab. Also, the necessity of therapeutic drug level monitoring in the maintenance phase will make it infeasible to blind the tacrolimus and sirolimus.

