#### 3.10.2 *Serious adverse events*

Serious adverse events (SAEs) are defined as those adverse events that:

- result in death;
- are life-threatening;
- require in-patient hospitalisation or prolongation of existing hospitalisation;
- result in persistent or significant disability or incapacity;
- are a congenital anomaly or birth defect following maternal or paternal exposure;
- are important medical events in the opinion of the responsible investigator (i.e. any event that is not immediately life-threatening and does not result in death or hospitalisation but which may jeopardise the patient or may require intervention to prevent one or the other outcomes listed above).

In addition, the following events will be recorded as Serious Adverse Events in this protocol.:

- cancers (including post-transplantation lymphoproliferative disorder)
- transplant biopsies
- rejection episodes
- loss of graft
- opportunistic infections such as cytomegalovirus and BK virus
- deliberate overdose of study treatment

All reports of SAEs will be entered on the IT system and those that are potential study endpoints will be reviewed, verified and coded (see section 3.12). SAEs that are not considered due to study treatment will be processed in a manner that allows the Coordinating Centre to provide information on such events for regulatory processes in accordance with current timelines.

---

 Such as stipulated in the European Clinical Trial Directive (Article 18 of Directive 2001/20/EC).

Information about the occurrence of study outcomes and all other serious adverse events (SAEs) will be sought at scheduled visits (for the first year after transplantation) and from national and other registries (including, but not limited to the Medical Records Information Service [MRIS], Hospital Episode Statistics, the UK Renal Registry, the Scottish Renal Registry).

The following minimum information will be collected for all SAEs:

- the unique Study Identification Number (Study ID) for the participant;
- the unique SAE Form Identification Number (SAE Form ID);
- the time and date that the SAE Form is completed;
- the source of the report (e.g. patient, relative, friend, etc.);
- a description of the event (e.g. myocardial infarction, pneumonia);
- the reason for believing the adverse event to be serious (e.g. death, life-threatening, hospitalisation, disabling, congenital anomaly in offspring, other important medical condition);

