### 4.3 Appendix 3: Transplant management

#### 4.3.1 Clinical management decisions

As far as possible, general management of the patient (including rejection episodes, medical and surgical complications, side effects of treatments) remains the responsibility of the doctors responsible for patient care, and this study does not impose unnecessary restrictions on such clinical management decisions.

 If mycophenolate sodium cannot be prescribed for local reasons, a dispensation can be made to allow mycophenolate mofetil to be substituted (see Appendix 9: Mycophenolate dosing for equivalent dosing).

In the case of rejection episodes, a biopsy would be strongly encouraged but not required by this protocol.

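### The SAP's comparison of first serious adverse events includes every transplant biopsy, so part of it will reflect how often unblinded doctors choose to biopsy

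*SAP*

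**What the plan says.** Protocol 3.10.2 gives six general criteria for seriousness and then extends them: "In addition, the following events will be recorded as Serious Adverse Events in this protocol". One entry on the added list is "transplant biopsies", with no limit by indication, finding or complication.

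SAP 2.2 opens its list with "The secondary comparisons will be of the incidence of the first occurrence (after maintenance randomisation) of". Item iii.e of that list, under other outcomes of interest, is "Serious adverse events (subdivided into respiratory, gastrointestinal, hepatobiliary, cardiovascular, musculoskeletal, skin, genitourinary, haematological, other transplant-related, other/unspecified". The SAP does not say whether biopsies belong in iii.e, which category would hold them, or whether an overall count will be shown beside the categories.

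On who decides to biopsy, protocol 4.3.1 leaves general management to the treating doctors and says of rejection episodes that "a biopsy would be strongly encouraged but not required by this protocol". The schedule in protocol Appendix 6 contains no protocol biopsies. Protocol 2.2 states: "Study medications will not be blinded as this will not be practical".

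**The concern.** A biopsy is a diagnostic act. When each one is an SAE by definition, a biopsy with a normal result counts the same as a harmful event. In an open trial the people ordering biopsies know whether the patient was converted to sirolimus. If their threshold differs by arm, the SAE comparison will show a difference that is not a difference in harm.

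The first-event rule adds a second problem. Within the category that holds biopsies, a normal biopsy can be the participant's first event and so displace a later genuine event of that category.

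The biopsy rate also bears on the rejection outcomes. Protocol Appendix 1 defines presumed rejection to include treated episodes with no biopsy, so readiness to biopsy can move an episode between presumed and biopsy-proven. The SAP lists no comparison of biopsies by arm that would let a reader judge this.

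**Working it through.** **Does anything in the plan remove biopsies from iii.e?**

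- SAP 2.2 iii.e states no exclusion.
- SAP 3.1 counts the first relevant event that adjudication has not refuted. A biopsy that took place cannot be refuted, and 'relevant' is not defined for SAEs.
- Protocol 3.12.2 has a panel review all SAEs, but gives no rule for setting biopsies aside.
- SAP 2.3 adds exploratory SAE analyses, which leave iii.e as it is.

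Nothing removes them.

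**How large could the effect be?** The plan gives no SAE rate, biopsy rate or power for this comparison, so there is no figure to reproduce. All rates below are assumptions.

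Let s be the risk of at least one non-biopsy SAE, equal in both arms, and b the risk of at least one biopsy. If the two are independent,

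P(any SAE) = 1 − (1 − s)(1 − b), and the difference between arms = (1 − s) × (difference in b).

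| s | b, lower arm v higher arm | Any SAE, lower v higher | Difference |
|---|---|---|---|
| 40% | 20% v 30% | 52% v 58% | 6 points |
| 40% | 30% v 40% | 58% v 64% | 6 points |
| 60% | 20% v 30% | 68% v 72% | 4 points |
| 60% | 30% v 40% | 72% v 76% | 4 points |

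First row: 1 − 0.6 × 0.8 = 0.52 and 1 − 0.6 × 0.7 = 0.58.

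**Without independence.** Let q be the share of biopsied patients who have no other SAE. Then P(any SAE) = s + bq and, with s and q equal in both arms, the difference is q × (difference in b). Independence is the case q = 1 − s. For a 10-point gap in biopsies, q = 0.6 gives 6 points, q = 0.4 gives 4, q = 0.1 gives 1 and q = 0 gives none.

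**Chance of a nominally significant result.** This keeps independence and uses a two-sided 5% test of two proportions with 200 to 400 patients per arm. The ceiling of 400 is half of the 800 recruited; the documents give no number for the second randomisation. The hazard ratio is ln(1 − p2)/ln(1 − p1), where p1 and p2 are the any-SAE risks.

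- s = 40%, biopsy 10% v 20%: any SAE 46% v 52%, hazard ratio ln(0.48)/ln(0.54) = 1.19, chance of significance 22% at 200 per arm and 40% at 400.
- Over s = 20% to 60% and biopsy 10% v 15%, 10% v 20% or 15% v 30%: hazard ratio 1.06 to 1.50, chance 6% to 94%.
- A category made up only of biopsies, 10% v 20%: chance 80% at 200 per arm and 98% at 400.

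The distortion is greatest where other SAEs are few, and so greatest in the category that holds the biopsies.

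**The case against.** The best case for leaving the SAP alone has four parts.

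1. **No overall total is promised.** For rejection, infection and cancer the SAP asks for 'all'; for SAEs it does not. The iii.e categories omit infection, cancer, rejection and graft failure, so the item may simply hold the remaining events by type. This stands as a reading: an overall count is possible but not stated. It does not remove the problem, because biopsies would then sit in one category, where they weigh most. That category is probably 'other transplant-related', though the SAP does not say so.
2. **Differential biopsy is assumed.** This also stands. The meta-analysis in protocol 1.3 reports no difference in acute rejection between sirolimus and calcineurin inhibitors, and no sentence says that doctors will biopsy converted patients more readily. A difference in biopsies could also reflect real differences in graft function. Hence 'partly'.
3. **Biopsied patients often have another SAE.** Rejection episodes are themselves on the protocol's added list, and some biopsies will accompany an admission. This can take the effect on an overall count to zero, but not the effect within the category that holds biopsies.
4. **The plan has other protections.** SAP 3.3 promises allowance for the nature of events, SAP 2.2 compares presumed and biopsy-proven rejection together, and protocol 2.3.4 costs biopsies as a resource. These help a careful reader, but they neither take biopsies out of iii.e nor commit the SAP to reporting them by arm beside rejection.

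A reader might also infer that CMV and BK findings should be dropped from iii.e for the same reason. The documents do not support that. The SAP counts both by name under opportunistic infections and gives iii.e no infection category. Protocol Appendix 1 requires symptoms as well as a positive assay for CMV syndrome; only BK infection rests on PCR alone.

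**Conclusion.** The point holds for any overall SAE count and for whichever iii.e category holds biopsies. As defined, both put a discretionary, unblinded clinical decision into a prespecified secondary comparison.

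Two stronger readings are tempting and should not be drawn. The first is that the trial's safety comparison as a whole is compromised: the SAP's named safety outcomes are serious infections and cancer, which biopsies do not enter, and the primary eGFR comparison is untouched. The second is that sirolimus will be made to look worse: the documents do not establish the direction, or that biopsy practice will differ at all.

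The size is likewise unknown. The figure of 4 to 6 points rests on an assumed 10-point gap in biopsy rates, an assumed 40% to 60% risk of other SAEs, and independence of the two. It falls towards zero if biopsied patients mostly have another SAE anyway.

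**What to change.** In SAP 2.2 iii.e, state that an event recorded only because a transplant biopsy was done is excluded from the SAE comparison, and that an event arising from a biopsy, such as a complication, still counts. Repeat the comparison with biopsies included as a sensitivity analysis. Beside the rejection outcomes, add a row giving, by arm, the number of participants with at least one transplant biopsy and the number of biopsies.

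Identify biopsies from the event description, which protocol 3.10.2 requires for every SAE. Do not rely on the other required field, "the reason for believing the adverse event to be serious". Its examples include hospitalisation and other important medical conditions but no code for protocol-listed events, so a biopsy could be filed under either.

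The cost is SAP wording and some recoding of SAE descriptions. Biopsy capture will be less complete after year one, when protocol 3.6 relies on registries and annual questionnaires, and the report should say so. Safety reporting to the coordinating centre and patient management stay unchanged.
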